#### 7.4 Multicenter studies

The clinical study Protocol doesn't contain information about the number of centers.

Data from all centers will be merged and analyzed as one population for all study endpoints.

#### 7.5 Multiple comparisons

No adjustments for multiplicity are required.

### 8 Summary of study data

Each study variable will be analyzed for relevant population.

Unless otherwise specified all raw data will be listed and sorted by unique subject identifier and study period/assessment (i.e. time point), where applicable.

Demographic characteristics, baseline variables, concurrent illnesses and medical conditions, prior and concurrent medications will be reported for *the core population (CP)*, *the target population (TP)* and *the safety population (SP)*.

The results will be reported overall and for scheduled treatment combination ( $\pm$  Dasabuvir,  $\pm$  RBV) and duration (12 or 24 weeks) groups.

Additionally and only for *the core population (CP)* the results will be presented for the CP analysis groups by the following parameters:

- HCV genotype and subtype (1a or 1b);
- fibrosis status (the Child Pugh Score class: A, B or C);
- treatment experienced or naïve patients (with/without prior treatment for CHC).

 Parameter "HCV Genotype and Subtype" from eCRF form "CHC DISEASE CHARACTERISTICS".

 Parameter "Class" in section "Child Pugh Score" from eCRF form "Liver fibrosis stage".

 Parameter "Prior treatment for CHC?" from eCRF form "MOST RECENT PRIOR THERAPY FOR CHC".

## 8.1 Subject Disposition

Subject disposition will be represented in tables and listings for *all patients who signed the Consent for use/disclosure of data form (informed consent)* and will include the following results:

- the number of subjects who signed the Consent for use/disclosure of data form;
- the number of subjects in each analyzed population;
- the number of subjects who has HCV RNA assessment performed at least 10 weeks post-treatment (i.e.  $\geq 70$  days after EoT);
- the number of subjects without HCV RNA assessment performed at least 10 weeks post-treatment (i.e.  $\geq 70$  days after EoT) and the reasons of it;
- the number of patients with the violations of the eligibility criteria and the corresponding violated inclusion/exclusion criteria.

## 8.2 Protocol Deviations

The presentation of Protocol deviations is not planned in this study.

## 8.3 Demographic characteristics

Descriptive statistics will be displayed in accordance with section 7.1 for the following demographic characteristics:

- gender;
- race/ethnic origin;
- height;
- weight;
- BMI.

All corresponding listings will be presented.

## 8.4 Baseline variables

Tables with descriptive statistics in accordance with section 7.1 will be presented for the following parameters, which are evaluated on baseline visit:

- duration of HCV infection diagnosis (in years);
- IL28B genotypes;
- HCV genotype and subtype;
- presence of prior treatment of CHC;
- most likely mode of HCV infection;
- liver fibrosis diagnostic method;
- liver biopsy diagnostic results (staging by histopathological scoring system):
  - ISHAK fibrosis score;
  - METAVIR fibrosis score;
  - BATTIS/LUDWIG fibrosis score;
  - KNODELL fibrosis score;
  - SCHEUER fibrosis score;

---

 Body mass index will be calculated as weight (kg) / [height (m)].

 This parameter will be calculated as (year of signed the informed consent – year of HCV infection diagnosis).

- FibroScan results (kPa);
  - FibroTest;
  - presence of esophageal varices;
  - history of liver decompensation;
  - Child Pugh score:
    - points;
    - classes;
  - liver decompensation characteristics:
    - current signs/symptoms of liver decompensation;
  - cirrhosis characteristics:
    - total bilirubin,  $\mu\text{mol/l}$  (mg/dl);
    - serum albumin, g/dl;
    - prothrombin time, prolongation (secs);
    - ascites;
    - hepatic encephalopathy;
  - outpatient hospitalizations:
    - number of hospitalization periods in the 4 weeks prior to starting the ABBVIE REGIMEN;
    - duration of each hospitalization periods (in days);
    - technical interventions performed in each hospitalization period;
    - symptoms treated in each hospitalization period;
  - outpatient consultations:
    - number of consultations in the 4 weeks prior to starting the ABBVIE REGIMEN;
    - technical interventions performed in each hospitalization period;
    - symptoms treated in each hospitalization period;
  - alcohol consumption:
    - alcohol use;
    - number of units/drinks per week (for patients who regular use alcohol);
- All corresponding listings will be presented.

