8.2.2 Secondary Objectives

2. To provide real world evidence for predictive factors of virological response

3. To collect information on co-morbidities and concomitant medication in the Russian population
4. To describe the tolerability of the ABBVIE REGIMEN ± RBV
5. To document the effect of the ABBVIE REGIMEN ± RBV on PROs and work productivity in the Russian population
6. To determine the impact of the ABBVIE REGIMEN ± RBV on healthcare resource utilization

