9.4.1.2 During Treatment Documentation

Follow-up visits are scheduled by the physician per routine clinical practice. Likewise treatment, procedures and diagnostic methods will follow physicians' routine clinical practice.

The following will be documented:

- Laboratory data

Key clinical chemistry	Remarks
▪ ALT	including ULN
▪ AST	including ULN, APRI and FIB-4 will be calculated
▪ γ-GT	
▪ Total bilirubin	
▪ Creatinine	creatinine clearance will be calculated
Key hematology	
▪ Hb	
▪ Platelets	
Virology	
▪ HCV RNA	quantitative/ qualitative HCV RNA PCR test, see 9.4.1.4
HIV-infected patients only	
▪ CD 4 count	most recent assessment
▪ HIV RNA	in copies/mL

- Concomitant medication, see 9.4.1.5
- Adherence to ABBVIE REGIMEN ± RBV (ABBVIE REGIMEN - % of target dose taken and RBV Y/N)
- Tolerability (sAEs and AEs, see 11.5) and pregnancies (see 11.6)
- Patient questionnaires see 9.4.1.6
- PSP satisfaction and utilization questionnaires; PAM-13
- Treatment related health care resource utilization

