9.4.1.3 Post-Treatment Documentation

Follow-up visits are scheduled by the physician per routine clinical practice. Likewise treatment, procedures and diagnostic methods will follow physicians' routine clinical practice.

Confidential Information

No use or disclose outside AbbVie is permitted without prior written authorization from AbbVie

Version 3.0 (22 Apr 2015) – country v 1.0 dated 26.06.2015

Page 26 of 61

The following will be documented:

- Laboratory data

Key clinical chemistry	Remarks
▪ ALT	including ULN
▪ AST	including ULN, APRI and FIB-4, will be calculated
▪ γ-GT	
▪ Total bilirubin	
▪ Albumin	
▪ Creatinine	creatinine clearance will be calculated
Key hematology	
▪ Hb	
▪ Platelets	
▪ Prothrombin time	or INR
Virology	
▪ HCV RNA	quantitative/ qualitative HCV RNA PCR test, see 9.4.1.4
HIV-infected patients only	
▪ CD 4 count	most recent assessment
▪ HIV RNA	in copies/mL

- Tolerability (sAEs, see 11.4) and pregnancies (see 11.6)
- Patient questionnaires see 9.4.1.6
- PSP Satisfaction and utilization questionnaires

Confidential Information

No use or disclose outside AbbVie is permitted without prior written authorization from AbbVie

Version 3.0 (22 Apr 2015) – country v 1.0 dated 26.06.2015

Page 27 of 61

Table 2 - Data Documentation Schedule

Assessment/ Procedure (only available data to be collected; no diagnostic or monitoring procedures to be applied to the patients apart from those of routine clinical practice)	Baseline	Treatment Period			Post-treatment (PT) Period		
		On-treatment visits	Mid treatment visit for pts receiving 24 weeks of therapy	EoT ^b	Early PT visit	SVR 12 visit	SVR 24 visit
Informed Consent	X ^a						
Demographic information	X						
IL28B	X						
Relevant CHC disease characteristics	X						
Liver fibrosis stage	X						
CHC treatment history	X						
HCV genotype and subtype	X						
HCV RNA samples	X	X	X	X	X	X	X
Clinical chemistry and hematology	X	X	X	X	X	X	X
ABBVIE REGIMEN initiation documentation	X						
ABBVIE REGIMEN adherence		X	X	X			
Concomitant medication	X	X	X	X			
Relevant medical history, co-morbidities	X						
sAE, AE and pregnancy reporting	X	X	X	X	X ^c	X ^d	X ^d
For patients receiving RBV: Evidence, in accordance with local label, that female patient or female partner of male patient is not pregnant	X						
Patient questionnaires – WPAI, EQ5D-5L	X			X		X	X
Patient questionnaires – PAM-13	X			X			
PSP evaluation		X	X	X	X	X	
Health care resource utilization	X	X	X	X			

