#### **3.1.2 Secondary Objectives**

The Protocol defines the following secondary objectives of this study:

- to provide real world evidence for predictive factors of virological response;
- to collect information on co-morbidities and concomitant medication in the Russian population;
- to describe the tolerability of the ABBVIE REGIMEN ± RBV;
- to document the effect of the ABBVIE REGIMEN ± RBV on patient-reported outcomes (PROs) and work productivity in the Russian population;
- to determine the impact of the ABBVIE REGIMEN ± RBV on healthcare resource utilization.

---

 This section is based on the sections 8 “Research Question and Objectives”, 9.3 “Variables”, 9.7.3.1 “Primary Effectiveness Endpoints” and 9.7.3.2 “Secondary Effectiveness Endpoints” of clinical study Protocol.

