### **13 Other analyses**

No other analyses will be performed in this study.

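### Healthcare resource utilization is a secondary objective, but the SAP summarises it only for the 4 weeks before treatment, so no planned table can address it

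*SAP*

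**What the plan says.** **Objective.** Protocol section 8.2.2 sets the aim "To determine the impact of the ABBVIE REGIMEN ± RBV on healthcare resource utilization", and the research question in section 8.1 also names resource utilization. SAP section 3.1.2 carries the objective over unchanged: "to determine the impact of the ABBVIE REGIMEN ± RBV on healthcare resource utilization".

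**Collection.** Protocol sections 9.4.1.1 (inclusion) and 9.4.1.2 (during treatment) both list "Treatment related health care resource utilization". In Protocol Table 2 the row "Health care resource utilization" is marked at baseline, on-treatment visits, the mid-treatment visit for 24-week patients, and EoT. No post-treatment visit is marked.

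**Analysis.** The SAP's resource-use variables are all in section 8.4, Baseline variables, which covers parameters "which are evaluated on baseline visit". They are the "number of hospitalization periods in the 4 weeks prior to starting the ABBVIE REGIMEN" and the "number of consultations in the 4 weeks prior to starting the ABBVIE REGIMEN", with hospitalization durations, interventions and symptoms treated. Table shells 1.9.1 and 1.10.1 use the same 4-week pre-treatment period. SAP section 13 then states: "No other analyses will be performed in this study".

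**The concern.** An impact of treatment on resource use cannot be read from counts taken before the first dose. At the least, a reader needs to see resource use during treatment, preferably beside the pre-treatment level. If the SAP is followed exactly, the report will describe how often patients were seen or admitted before they started, and no table will show what happened afterwards. A secondary objective that is also part of the research question would be left without a summarised result. Nothing in the SAP would warn the reader, because section 16 describes the methods as fully consistent with the protocol and names only the dropped regression for the patient support program.

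**Working it through.** The plan gives no figure for this objective, so the check traces it from objective to data to planned output.

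1. **Is the objective still live?** Yes. It is in Protocol 8.2.2 and SAP 3.1.2. The protocol numbers its secondary objectives 2 to 6, which makes five; this is the last.

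2. **What is scheduled for collection?** Table 2 marks four time points: baseline, on-treatment, mid-treatment (24-week patients only) and EoT. A 12-week patient has 4 − 1 = 3.

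3. **What is summarised?** One time point, baseline.

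| Time point | Marked in Protocol Table 2 | Summarised in the SAP |
|---|---|---|
| Baseline (4 weeks before start) | yes | yes: 8.4, Tables 1.9 and 1.10 |
| On-treatment visits | yes | no |
| Mid-treatment visit (24-week patients) | yes | no |
| EoT | yes | no |

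4. **Do the other shells fill the gap?** No. The remaining tables in the 1.9 and 1.10 series repeat the first by genotype, Child-Pugh class, prior treatment, treatment group or analysis population. None adds a time point.

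5. **Is it covered in another section?** SAP sections 9 (effectiveness), 10 (questionnaires) and 11 (safety) contain no resource-use variable. Section 13 rules out further analyses.

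6. **Would the data appear at all?** Possibly. SAP section 8 lists all raw data by default, so on-treatment records may appear in a patient listing. A listing is not a summary.

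7. **Where does the gap begin?** In the protocol. Section 9.3.2 does not list resource use among the secondary variables, and section 9.7 describes no resource-use analysis. SAP section 3.2.2 follows the protocol's list. The SAP had no analysis to elaborate, yet it kept the objective and did not record that it would go unanalysed.

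**The case against.** Several counter-arguments have weight.

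- **The data are not lost.** A reader might infer that the on-treatment data go unused. The documents do not support that. Raw data are listed by default. Some on-treatment use is also visible elsewhere: an adverse event leading to admission is an SAE (Protocol 11.1), treatment-emergent SAEs are tabulated (SAP 11.2), and so are concurrent medications (SAP 8.6). None of these gives consultations, hospital days or a utilization rate.

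- **The SAP follows the protocol.** It is meant to elaborate the protocol's analysis, and the supplied protocol has none for this objective. This stands as to origin. It does not excuse restating the objective and claiming full consistency.

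- **The governing documents are not to hand.** SAP section 2 says it was written from protocol version 4.0 (11 July 2017) and CRF version 2.0. The protocol supplied is version 3.0 (22 Apr 2015), country version 1.0. Whether the later versions still collect on-treatment resource use, and in what form, cannot be checked. This stands, and it limits what can be said about data availability.

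- **The lost follow-up cannot be sized in weeks.** It is tempting to say that 12 or 24 weeks of resource data per patient are left out. Table 2 marks visits only, its header restricts collection to available data, and no on-treatment recall period is given. Continuous coverage would be an assumption.

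- **An uncontrolled study cannot establish impact.** The 4 weeks before treatment may include work-up visits, and monitoring during treatment may itself generate consultations. This limits the interpretation of any before/during comparison. It is not a reason to have no on-treatment summary.

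**Conclusion.** The point holds as a gap in planned summaries. The SAP retains the objective, but its only resource-use tables stop at the start of treatment, and section 16 does not disclose this. Its size is one of five secondary objectives without a planned result, and one of four scheduled time points summarised (one of three for a 12-week patient). The primary endpoint and its precision are unaffected.

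The finding that no planned table can address the objective rests on the SAP alone and is firm. That on-treatment data exist to be summarised rests on the supplied protocol and on the assumption that protocol version 4.0 and CRF version 2.0 kept that collection. A reader might also infer that the SAP dropped an analysis the protocol had specified; the supplied protocol specifies none, so the shortfall belongs to both documents.

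**What to change.** 1. **Add descriptive tables.** Model them on Tables 1.9 and 1.10, for each on-treatment window and EoT: consultations, hospitalizations, hospital days and interventions. Present them overall and by regimen group, next to the pre-treatment values. Amend SAP section 13 to match.

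2. **Standardise where the data allow.** The pre-treatment look-back is 4 weeks and treatment lasts 12 or 24, so raw counts are not comparable. If the eCRF recall period is known, express use per patient per 4 weeks, with within-patient change and a 95% CI. Name an interval method suited to rates or paired changes, such as a paired bootstrap. The SAP's default Clopper-Pearson interval (section 7.2) is for proportions and does not fit. If the recall period is not known, report on-treatment counts without a rate.

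3. **Label the comparison.** State that the before/during contrast is descriptive and uncontrolled, and that pre-treatment work-up and on-treatment monitoring visits affect the counts.

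4. **If the data were not captured.** If CRF version 2.0 holds no on-treatment resource use, state in SAP section 16 that the objective will not be analysed, and why.

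The cost is some SAP text and a few descriptive tables. No new data collection is needed if the CRF matches the supplied protocol. SAP section 2 allows revision before database soft lock; after that, the departure would be explained in the study report.

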### 8.5 Concurrent Illnesses and Medical Conditions

Medical history will be coded using the MedDRA version 20.0 (or further updating) and summarized by system organ class (SOC) and preferred term (PT) according to Data MATRIX LLC SOP [3] and will be presented in listings and tables.

Tables with descriptive statistics in accordance with section 7.1 will be presented for the following parameters, which are evaluated on baseline visit:

- presence of co-infection with other relevant diseases;
  - HIV characteristics:
    - CD4 T-cell count (for HIV co-infected patients);
    - HIV-RNA test results (for HIV co-infected patients);
  - liver and/or CHC related co-morbidities;
  - other co-morbidities.
- All corresponding listings will be presented.

## 8.6 Prior and Concurrent Medications

All medications will be coded using WHODD version Jun 2015 (or actual version on the time of the study completion) according to Data MATRIX LLC SOP [3]. Prior and concurrent medications will be presented in a separate listings and tables.

Prior medication will be determined using “MOST RECENT PRIOR THERAPY FOR CHC” flag in the CMCAT variable of CM domain of the database. Concurrent medications will be determined using “CO-MEDICATION” flag in the CMCAT variable of CM domain of the database.

The “treatment profile No” from “CO-MEDICATION” eCRF form will be presented in the separate listing.

All corresponding listings will be presented. Additionally listings will contain the following information for prior CHC therapy:

- presence of prior treatment for CHC;
- generic drug name;
- initial dose (by generic drug name groups and units groups);
- start frequency (frequency of drug administration at the start by generic drug name groups);
- duration (by generic drug name groups, in weeks);
- outcome of prior treatment.

## 9 Effectiveness analysis

Effectiveness analysis will be conducted on *the core population (CP)*, *the target population (TP)* and *the core population with sufficient follow-up data (CPSFU)*.

The results will be reported overall and for scheduled treatment combination ( $\pm$  RBV) and duration (12 or 24 weeks) groups. Additionally and only for *the core population (CP)* the results will be presented for the CP analysis groups by the following parameters:

- HCV genotype and subtype (1a or 1b);
- fibrosis status (the Child Pugh Score class: A, B or C);
- treatment experienced or naïve patients (with/without prior treatment for CHC).

Tables with descriptive statistics will be prepared in accordance with section 7.1. Confidence intervals will be presented according the section 7.2. All corresponding listings will be presented. Additional listings for *the non-core population (NCP)* will be created.

The following effectiveness endpoints will be analyzed:

- the percentage of patients achieving SVR12 (single last HCV RNA <50 IU/mL 12 weeks after the last actual dose of the ABBVIE REGIMEN);
- the percentage of patients with at least one and each of SVR12 non-response categories:
  - breakthrough (at least one documented HCV RNA <50 IU/mL followed by HCV RNA  $\geq$ 50 IU/mL during treatment);
  - failure to suppress (each measured on-treatment HCV RNA value  $\geq$ 50 IU/mL);

---

 Parameter “HCV Genotype and Subtype” from eCRF form “CHC DISEASE CHARACTERISTICS”.

 Parameter “Class” in section “Child Pugh Score” from eCRF form “Liver fibrosis stage”.

 Parameter “Prior treatment for CHC?” from eCRF form “MOST RECENT PRIOR THERAPY FOR CHC”.

